bone-related diseases (osteoarthritis, RA), and chronic pain states (chronic lower back pain, fibromyalgia), the latter of which is frequently associated with IC/BPS as NUAS. Based on Faraday's law, electromagnetic interactions (e.g. PEMF) with biological processes and conditions (e.g. IC/BPS) will theoretically address many of the proposed pathophysiological causes of the condition. While the mechanism(s) of action are not fully understood, PEMF therapy has been shown in several studies (randomized, double-blinded, placebo-controlled trials) to decrease the output of pro-inflammatory proteins, improve oxygenation of blood and tissue, stabilize transmembrane action potential and ion channels, and stimulate tissue regeneration¹²⁻¹⁵. Thus, PEMF may provide a safe, non-invasive therapeutic option that would be complementary to, or serve as an alternative for, the treatments that are currently being administered in IC/BPS for pain reduction. Of note, PEMF has demonstrated an excellent safety profile with no associated systemic risks reported to date¹⁶. Additionally, the application of exogenous PEMF to stimulate the pelvic floor muscle has recently been introduced for treating urge and/or stress urinary incontinence and overactive bladder¹⁷. Furthermore, if patient safety and efficacy for pain reduction are demonstrated, these feasibility studies will provide the foundation for larger multi-site trials to determine additional parameters regarding the appropriate number of treatments as well as the duration of benefit (pain relief) following treatments.

Objectives

The objective of this pilot study is to test the idea that PEMF therapy will serve as a safe, non-invasive therapeutic modality that can effectively improve the chronic pain and/or associated symptoms of IC/BPS patients. We hypothesize that PEMF therapy will result in significant pain reduction in IC/BPS patients, specifically those with a non-bladder centric phenotype.

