Published results from randomized, double-blinded, placebo-controlled clinical trials that have evaluated the efficacy of PEMF for pain management in conditions such as lower back pain, osteoarthritis, rheumatoid arthritis, and fibromyalgia have all reported significant pain reduction following PEMF therapy. Chronic pelvic pain and widespread, non-localized pain (beyond the bladder) are common findings in many IC/BPS patients. The proposed mechanism of action of PEMF therapy (increased microcirculation and tissue regenerative capacity through modulation of inflammatory processes) provides a compelling rationale for evaluating the efficacy of PEMF in IC/BPS patient pain relief.

Methods and Measures

Design

This is a single center clinical series evaluating symptom relief following a 4-week trial of PEMF therapy. From our registry of IC/BPS patients we will recruit women, ages 18-80, who

have met all inclusion and exclusion criteria, which includes demonstration of an anesthetic BC > 400 cc (non-bladder-centric phenotype) and a current numeric rating scale (NRS) pain score for pelvic pain ≥ 6 . Upon enrollment, each patient will be taught how to administer home treatment with the BEMER (Bio Electro Magnetic Energy Regulation) PEMF devices which consist of a total body mat (B.Body) plus a targeted pelvic mat (B.Pad). Following the brief in-clinic training, participants will be sent home with the PEMF devices (pre-set to deliver the same level of energy each time) and will self-administer 8 minute PEMF therapy sessions, twice daily (once in the morning, once in the evening).

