Patient assessments will occur at three time points: (1) enrollment, (2) after four weeks of treatment, and (3) at twelve weeks post-enrollment. The primary outcome measure will be the change in NRS pain score for pelvic pain. A decrease of at least 2 points on the NRS pain scale will be considered as representative of a significant decrease in pelvic (and/or widespread) pain. Secondary outcomes will be assessed by validated IC/BPS questionnaires (O'Leary-Sant indices), voiding characteristics (patient recorded voiding diary), change in perceived pain as determined by pain body maps, and the patient's overall impression of change (Global Response Assessment). Follow-up assessments will be completed remotely through phone or email surveys. During the twelve-week study, patients will not undergo any of the following IC/BPS therapies: cystoscopy with hydrodistention, bladder instillations, or trigger point injections. Patients that were prescribed a stable dose of pro re nata (PRN) narcotic medication at least three months prior to enrollment will be included in the study. Patients will be expected to report which, if any, pain medications they have been taking prior to enrollment and what additional medications they plan to use throughout the duration of the study. The following IC/BPS oral medications will be allowed during this time: amitriptyline, cimetidine, hydroxyzine, and pentosan polysulfate.

The demographic data will be extracted from patient's electronic medical record. The basic office evaluation will be composed of detailed medical history, physical exam, urinalysis, urine culture, 7-days voiding diary, O'Leary-Sant symptom and problem index (ICPI/ICSI), Pelvic Pain and Urgency/Frequency Patient Symptom (PUF) scale, Genitourinary Pain Index (GUPI), SF-36 quality of life questionnaires, and numeric rating scale for pain in the last 24 hours.

In this proof of concept study, *all* participants will receive the full therapy (i.e. there will not be a control group). In the double-blind placebo-controlled crossover trial that will follow this proof-of-concept study, we will have access to placebo (sham) mats for use as a control.

Subject Selection Criteria

Participants will be recruited from the Urology Clinic at Wake Forest Baptist Hospital and all study participants will provide written informed consent.

- **Inclusion Criteria**

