Female patients between 18 to 80 years with a previously established clinical diagnosis of IC/BPS. Participants must have an anesthetic BC > 400 cc, a current NRS score ≥ 6 , and have no cognitive deficits. Patients will be required to attest that they will not receive a new prescription and/or an increased dose of narcotic medication while participating in the study.

- **Exclusion Criteria**

Any history of bladder, uterine, ovarian, or vaginal cancer, urethral diverticulum, spinal cord injury, stroke, Parkinson's disease, multiple sclerosis, spina bifida, radiation cystitis, cyclophosphamide treatment, immunosuppressive therapy in consequence of transplantation, allogeneic cellular transplantation, or bone marrow or stem cell transplantations, deep vein thrombosis, or genital herpes. Patients will be excluded from this study if they have an implanted pace-maker, metal prosthesis, urinary tract infection, BMI > 40, or are currently pregnant.

- **Sample Size**

For this small pilot study, we will enroll up to 10 study patients with the goal of achieving a full dataset from at least 6 patients.

Human Subjects Protection

Informed Consent: An IRB-approved written informed consent will be obtained from each subject. Patients will initially be contacted and introduced to the study via phone call from a study team member to discuss study details and answer questions. If they agree, an electronic copy of the IRB-approved consent form will be e-mailed to the patient. Informed consent and signature will be acquired in the Wake Forest University Urology Outpatient Clinic prior to training on the PEMF device.

Confidentiality and Privacy: Confidentiality will be protected by collecting only information needed to accomplish future demographic matching (i.e. patient's age, ethnicity, BMI, etc.), minimizing to the fullest extent possible the collection of any information that could directly identify subjects, and maintaining all study information in a secure manner. To help ensure subject privacy and confidentiality, a unique study identifier will appear on the data collection form. Any collected patient identifying information corresponding to the unique study identifier will be maintained on a separate master log. The master log will be kept secure, with access limited to designated study personnel. Following data collection, subject identifying information will be destroyed at the earliest opportunity consistent with data validation and study design,

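### The implant exclusion names a pacemaker and a metal prosthesis but, read literally, admits patients with other active implanted devices, and any change to such a device goes unrecorded

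*Combined protocol and SAP*

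**What the plan says.** Under Subject Selection Criteria, Exclusion Criteria, the current-state exclusions begin: "Patients will be excluded from this study if they have an implanted pace-maker, metal prosthesis". The sentence goes on to urinary tract infection, a BMI above 40 and current pregnancy. The other exclusions in that section are past diagnoses and treatments. None refers to a device, and the documents contain no general term for active or electronic implants.

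Methods and Measures, Design, describes the exposure as "PEMF devices which consist of a total body mat (B.Body) plus a targeted pelvic mat (B.Pad". After brief training in clinic, participants go home and "will self-administer 8 minute PEMF therapy sessions, twice daily (once in the morning, once in the evening", for four weeks. Assessments are at enrollment, after four weeks of treatment and at twelve weeks, and follow-up is remote.

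On other treatment, the same section says that "patients will not undergo any of the following IC/BPS therapies: cystoscopy with hydrodistention, bladder instillations, or trigger point injections". It also says: "Patients will be expected to report which, if any, pain medications they have been taking prior to enrollment", and asks which additional medications they plan to use. Four oral drugs are allowed, and narcotic use must be stable. Device therapy is not mentioned.

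On screening: "The basic office evaluation will be composed of detailed medical history, physical exam", followed by laboratory tests, a voiding diary and questionnaires. The primary outcome is the change in pelvic pain NRS, there is no control group, and the Objectives include safety.

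**The concern.** The protocol excludes one kind of electronic implant from an electromagnetic treatment and does not mention the others. A defibrillator, a nerve or spinal cord stimulator and an implanted drug pump are not pacemakers. On an ordinary reading they are not metal prostheses either. A study team that applies the list as written would enroll such a patient.

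Two things are at stake. First, safety is part of the objective, sessions are unsupervised, and no assessment is scheduled between enrollment and the end of the treatment month. Secondly, a stimulator or pump may itself be a treatment for pain or bladder symptoms. If its action changed during the study, pelvic NRS and voiding could change with it. A single-arm series has no comparison that would show this.

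**Working it through.** The plan gives no figure on this point. The check is therefore mainly of the text, with a small illustration of scale.

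**Step 1. Does any text close the gap?**

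| Place | What it covers | Does it reach other active implants? |
|---|---|---|
| Exclusion Criteria | Pacemaker, metal prosthesis | Not on a literal reading |
| Inclusion Criteria | Age, diagnosis, bladder capacity, NRS, cognition, narcotic attestation | No |
| Design, barred therapies | Three procedures | No |
| Design, reporting by patients | Medications | No |
| Design, office evaluation | History and physical exam | May reveal an implant, but no rule then applies |
| Data and Safety Monitoring; Reporting | Oversight by the investigator; prompt reporting of events | Acts after an event, not at entry |

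Nothing closes it.

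**Step 2. When would an implant affect the primary outcome?** Assume that the device contributes additively to NRS: c0 at baseline and c1 at follow-up. With underlying scores B and F, the observed change is

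(F + c1) − (B + c0) = (F − B) + (c1 − c0).

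If the settings are constant and the field does not affect the device, c1 = c0 and the device drops out. If it is started, reprogrammed, switched off or disturbed, the change shifts by d = c1 − c0, in either direction. The Design section neither prevents nor records this.

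**Step 3. Weight of one patient.** Inputs: up to 10 enrolled and at least 6 with full data (Sample Size); a decrease of 2 points or more counts as significant (Design). The range d = 2, 4, 6 is an assumption.

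- Shift in mean change = d/n.
  - n = 6: 2/6 = 0.33, 4/6 = 0.67, 6/6 = 1.00.
  - n = 10: 2/10 = 0.20, 4/10 = 0.40, 6/10 = 0.60.
- Shift in the proportion reaching the 2-point threshold, if that patient crosses it = 1/n: 16.7 percentage points at n = 6, 10 at n = 10.

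**Step 4. Chance of enrolling at least one such patient.** The documents give no prevalence q, so 2%, 5% and 10% are assumptions. Formula: 1 − (1 − q)^n.

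| q (assumed) | n = 6 | n = 10 |
|---|---|---|
| 2% | 11% | 18% |
| 5% | 27% | 40% |
| 10% | 47% | 65% |

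Steps 3 and 4 show scale only. The figures in Step 3 would apply to any one patient whose score moved for an unrelated reason.

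**The case against.** The strongest reply is that little about the risk can be established from the documents, and much of it stands.

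- **A reader might infer that a stimulator is a confounder simply by being present.** It is not. At constant settings it is there at both assessments and cancels from the change.
- **A reader might infer a demonstrated hazard.** The documents give no field strength, labelling or contraindications for the mats, and do not say why pacemakers and metal prostheses are excluded. The sentence that begins "Based on Faraday's law, electromagnetic interactions (e.g. PEMF) with biological processes and conditions (e.g. IC/BPS" concerns biological processes, so it does not show that the field acts on implants.
- **A reader might picture the device lying directly under the pelvic mat.** The Design section calls that mat targeted but does not describe its position.
- **A reader might count 2 × 28 = 56 sessions delivered over the implant.** That is the nominal session count for every participant. It says nothing about where an implant lies.
- **Nothing shows that any registry patient has such an implant.**

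There are also partial safeguards. This is one center recruiting from its own registry, with a history and physical exam, oversight by the investigator and prompt reporting. An attentive investigator might well stop before enrolling such a patient.

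These points limit the size of the concern, but they do not supply the missing rule. The criteria still exclude one electronic implant, are silent on the rest and give no reason for the difference.

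**Conclusion.** The point holds as a gap and an inconsistency in the eligibility text. As written, patients with active implants other than a pacemaker can be enrolled into unsupervised home treatment. This rests on reading metal prosthesis in its ordinary sense, which the documents do not extend to electronic devices.

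The safety consequence cannot be sized from the documents. The effect on the primary outcome is conditional: it needs such a patient to be enrolled and the device's action to change within the twelve weeks. If both happen, one patient can move the mean change by up to 1.00 point with 6 complete patients or 0.60 with 10, under the assumed shift of at most 6 points. The claims that such an implant necessarily biases the result, or that harm is shown, go beyond the documents.

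It is worth correcting before enrollment because it changes who can enter, bears on a stated objective and costs little.

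**What to change.** 1. In the Exclusion Criteria, widen the pacemaker term to active implanted electronic devices as a class, with examples such as defibrillators, nerve or spinal cord stimulators and drug pumps. The sponsor should confirm the scope against the device labelling, which is not in the documents, and give a reason for any device left eligible.
2. Check the criterion in the medical history already taken at the office evaluation.
3. For any implant that stays eligible, add neuromodulation and setting changes, with dates, to what is recorded under Design over the twelve weeks. Asking every participant the same question would also catch a device started after enrollment, which an entry criterion cannot.

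The cost is one phrase in the criteria, one item in the history and one question at each follow-up contact. The downside is that an occasional registry patient is not enrolled, which matters a little when the target is 6 to 10.

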producing an anonymous analytical data set. Data and records will be kept locked and secured, with access limited to study staff and password protection on all data stored electronically. No reference to any individual participant will appear in reports, presentations, or publications that may arise from this study.

Every effort will be made to maintain participant privacy. Data will only be released to scientists who are qualified and prepared to conduct a research study. If publications or presentations result from this research, participants will not be identified by name or any other personal identifier.

Data and Safety Monitoring

The principal investigator and study coordinator will be responsible for the overall monitoring of the data and safety of study participants and will ensure that the subjects' information is not revealed. The principal investigator will be assisted by other members of the study staff.

Reporting of Unanticipated Problems, Adverse Events or Deviations

Any unanticipated problems, serious and unexpected adverse events, deviations, or protocol changes will be promptly reported by the principal investigator or designated member of the research team to the IRB and sponsor or appropriate government agency if appropriate.

References

1. Van de Merwe JP NJ, Bouchelouche P, Bouchelouche K, Cervigni M, Daha LK, Elneil S, Fall M, Hohlbrugger G, Irwin P, Mortensen S, van Ophoven A, Osborne JL, Peeker R, Richter B, Riedl C, Sairanen J, Tinzi M, Wyndaele JJ. Diagnostic criteria, classification, and nomenclature for painful bladder syndrome/interstitial cystitis: an ESSIC proposal. *Eur Urol*. 2008;53(1):60-67.
4. Parsons CL. "The role of leaky epithelium and potassium in the generation of bladder symptoms in interstitial cystitis/overactive bladder, urethral syndrome, prostatitis and gynaecological chronic pelvic pain." *BJUI*. 2010 (107): 370-375.

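### No safety contact is planned during the four weeks of home treatment, so in that period the named monitors depend on spontaneous reports

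*Combined protocol and SAP*

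**What the plan says.** The Design section describes the study in one line: "This is a single center clinical series evaluating symptom relief following a 4-week trial of PEMF therapy". On setting it says: "Following the brief in-clinic training, participants will be sent home with the PEMF devices". Each session lasts 8 minutes and there are two a day. The devices are pre-set to the same energy each time.

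The visit schedule, also under Design, is: "Patient assessments will occur at three time points: (1) enrollment, (2) after four weeks of treatment, and (3) at twelve weeks post-enrollment". The two follow-up assessments are done remotely by phone or email survey. The outcomes listed there are pain, questionnaires, voiding characteristics, body maps and a global response rating. Adverse events are not among them.

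On numbers, Sample Size says "we will enroll up to 10 study patients with the goal of achieving a full dataset from at least 6 patients".

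On oversight, Data and Safety Monitoring says "The principal investigator and study coordinator will be responsible for the overall monitoring of the data and safety of study participants", with help from other study staff. The next section adds: "Any unanticipated problems, serious and unexpected adverse events, deviations, or protocol changes will be promptly reported by the principal investigator" or a designated team member, to the IRB and, where appropriate, to the sponsor or a government agency. Neither section says when safety information is gathered or reviewed.

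Safety is named in Objectives. The Background section makes larger multi-site trials depend on the result: "if patient safety and efficacy for pain reduction are demonstrated".

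**The concern.** A study that sets out to test whether a therapy is safe should plan to learn about safety while people are receiving it. Here the plan assigns responsibility for monitoring, but its schedule gives the responsible staff nothing to look at between device training and the end of treatment. Whatever they learn in that window depends on a patient deciding to call.

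Two things are at stake. The first is patient protection: a tolerability problem that a patient does not volunteer stays unknown until her exposure is over. The second is the quality of the safety result. Milder events are recalled over four weeks, if they are asked about at all, and the series is meant to inform larger trials.

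**Working it through.** **Inputs.** Up to 10 enrolled, with at least 6 full datasets (Sample Size). Four weeks of treatment, two 8-minute sessions a day at home, and assessments at enrollment, after four weeks and at week 12 (all Design). The plan gives no safety threshold, event rate or power calculation, so there is no planned figure to reproduce.

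**Step 1: exposure before the first planned follow-up contact** (assuming 28 days and full adherence).
- Sessions per woman: 2 × 28 = 56, or 56 × 8 = 448 minutes.
- Sessions across the series: 56 × 10 = 560.
- Planned contacts between training and the end of those sessions: 0.

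**Step 2: what the oversight text adds.** Setting the schedule beside the two oversight sections:
- Who monitors: stated.
- Onward reporting of serious and unexpected events: stated, and it takes effect once the team knows of an event.
- How or when the team finds out during home treatment: not stated in the supplied text.
- When accumulating safety data are reviewed: not stated.

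**Step 3: what one call changes.** As an illustration only, a call at the midpoint would cut the longest interval without planned contact during treatment from 28 days to 28 / 2 = 14 days. Events after the call would still be picked up only at the week-4 assessment, or spontaneously.

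**Step 4: what it does not change.** With zero events, the one-sided 95% upper bound on the event rate is 1 − 0.05^(1/n):
- n = 10: 1 − 0.05^(1/10) = 25.9%.
- n = 6: 1 − 0.05^(1/6) = 39.3%.

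Better event capture makes the safety data more credible but does not let a series of this size establish safety.

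**Step 5: expected numbers harmed, as illustration only.** The documents give no harm rate, so every value of p below is an assumption. The columns are: all 10 treated with no hold (10p); one review after 3 patients, the other 7 starting only if no event has been seen (3p + 7p(1−p)³); and strictly one-at-a-time starts, held at the first event (1 − (1−p)^10).

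| p | No hold | Review after 3 | One at a time |
|---|---|---|---|
| 1% | 0.100 | 0.098 | 0.096 |
| 5% | 0.50 | 0.45 | 0.40 |
| 10% | 1.0 | 0.81 | 0.65 |
| 20% | 2.0 | 1.32 | 0.89 |
| 30% | 3.0 | 1.62 | 0.97 |

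Both right-hand columns assume that events are known in time and that a hold rule exists. The safety call by itself has neither property, so the table does not measure its benefit. It shows how far any such benefit depends on the assumed rate: at 1% it nearly vanishes.

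**The case against.** The strongest reply is that the text already provides oversight suited to a very small pilot of a low-risk device. Named staff are responsible, and serious and unexpected events must be reported promptly. Nothing stops a patient from calling. The consent pages were removed from the supplied text, so any instruction on whom to contact cannot be judged. The Background reports no systemic risks to date, the energy is pre-set, patients are trained in clinic, and the criteria exclude pacemakers, metal prostheses, pregnancy and a history of deep vein thrombosis. Enrollment pace is not stated either, so week-4 data from early patients may well be available before later ones start.

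Most of this stands. A reader might infer from the schedule that the monitors cannot act on a harm while patients are exposed. The documents do not support that, because a spontaneous report can reach the team at any time and the reporting duty then applies. A reader might also infer that the whole cohort will be treated before anyone looks. That too is unsupported without an enrollment pace. Nor do the documents support harm rates of 10% to 30%, least of all for serious events.

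What the reply does not remove is the narrower gap. Spontaneous reporting is not planned monitoring, and a study with safety in its objective schedules no question about safety during exposure.

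**Conclusion.** The point holds in a limited form. During the four weeks of home treatment the principal investigator and coordinator have no planned safety information. Its size is best stated as exposure: 56 sessions per woman and up to 560 in the series, assuming 28 days and full adherence, with no scheduled contact. No number of harms prevented can be given, because the documents contain no event rate.

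This is a worthwhile low-cost improvement, not evidence of a hazard. The missing pause criterion and the lack of spacing between enrollments do not, on their own, make the design unsound for a pilot of at most 10 patients. The conclusion rests on the supplied text; contact instructions in the consent form could narrow the gap but would still leave it to the patient to start the report.

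**What to change.** Amend the assessment schedule under Design and the Data and Safety Monitoring section to state three things:

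1. The existing study coordinator makes one brief safety call to each patient during the four-week treatment period, in addition to the planned assessments.
2. Any adverse events reported on that call are recorded.
3. The principal investigator reviews these records as they accrue, before the week-4 assessments.

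Whether to add a pause criterion, and what it should be, is for the investigator and the IRB to define; none is proposed here. No new committee is needed.

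The cost is about 10 short calls (one for each of up to 10 patients) and a small amendment. The call does not alter the treatment, the outcome measures or the sample size.
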